6. ANALYSES AND SUMMARIES

6.1. Primary Endpoint(s)

6.1.1. Local Reactions and Systemic Events

6.1.1.1. Main Analysis

- Estimand strategy: Treatment policy ([Section 2.2.1](#)).
- Analysis set: Safety population ([Section 4](#)).
- Analysis methodology: 95% CI of the proportion of participants reporting each event, using the Clopper-Pearson method ([Section 5.2.1](#)).

- Analysis timing: Day 1 through Day 7 after vaccination.
- Intercurrent events and missing data: All data collected after the intercurrent events will be included ([Section 2.2.1](#)). The participants without any e-diary data or reactogenicity event data on the Participant Reported Reactogenicity CRF page throughout the 7 days after vaccination will be excluded from the analysis; intermediate missing values will not be imputed. Partially missing e-diary data are imputed as “no” ([Section 3.1.1](#), [Section 3.1.2](#), and [Section 5.3.1.1](#)); e-diary data that are confirmed as errors will not be used for analysis.

Reporting results:

- Descriptive statistics, including the proportion (%), the numerator (n) and the denominator (N) used in the proportion calculation, and the 95% CI for the percentage using the Clopper-Pearson method, will be presented for each study intervention group. The denominator will be the number of participants reporting at least 1 "yes" or "no" response for the local reaction after vaccination.
- Bar charts with the proportions of participants for each and any local reaction and each and any systemic event through the 7 days following vaccination will be plotted for each study intervention group. The bars will be divided into severity categories to highlight the proportions of participants by maximum severity.

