#### 10.11.8.10.4. Unscheduled Visit for a Grade 3 or Suspected Grade 4 Reaction

If a Grade 3 local reaction (Section 8.3.4.2), Grade 3 systemic event (Section 8.3.4.3), or fever  $\geq 39.0^{\circ}\text{C}$  ( $\geq 102.1^{\circ}\text{F}$ ) (Section 8.3.4.4) is reported in the reactogenicity e-diary, a telephone contact should occur to ascertain further details and determine whether a site visit is clinically indicated. If a suspected Grade 4 local reaction (Section 8.3.4.2), systemic event (Section 8.3.4.3), or fever  $> 40.0^{\circ}\text{C}$  ( $> 104.0^{\circ}\text{F}$ ) (Section 8.3.4.4) is reported in the reactogenicity e-diary, a telephone contact or site visit should occur to confirm whether the event meets Grade 4 criteria.

A site visit must be scheduled as soon as possible to assess the participant unless any of the following is true:

- The participant is unable to attend the unscheduled visit.
- The local reaction/systemic event is no longer present at the time of the telephone contact.
- The participant recorded an incorrect value in the reactogenicity e-diary (confirmation of a reactogenicity e-diary data entry error).
- The PI or authorized designee determined it was not needed.
- The investigator or appropriate designee confirmed severe reactogenicity assessment via medical records and/ or telehealth assessment.

This telephone contact will be recorded in the participant's source documentation and the CRF.

If the participant is unable to attend the unscheduled visit, or the PI or authorized designee determined it was not needed, any ongoing local reactions/systemic events must be assessed at the next study visit.

During the unscheduled visit, the reactions should be assessed by the investigator or a medically qualified member of the study staff, such as a study physician or a study nurse, as applicable to the investigator's local practice, who will:

- Measure oral temperature ( $^{\circ}\text{F}/^{\circ}\text{C}$ ).
- Measure minimum and maximum diameters of redness (if present).
- Measure minimum and maximum diameters of swelling (if present).
- Assess injection site pain (if present) in accordance with the grades provided in Section 8.3.4.2.

- Assess systemic events (if present) in accordance with the grades provided in [Section 8.3.4.3](#).
- Assess for other findings associated with the reaction and record these on the AE page of the CRF if appropriate.

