3.1.1. Local Reactions

The local reactions reported in the e-diary are pain at the injection site, redness, and swelling, from Day 1 through Day 7 after vaccination, where Day 1 is the day of vaccination.

If a local reaction persists beyond the end of the 7-day e-diary collection period following vaccination, the participant will be requested to report that information and the corresponding resolution date. The investigator will enter this resolution date on the Summary of Reactogenicity CRF page.

For missing records on local reactions during the 7-day e-diary collection period, the data may be retrieved by the investigator via participant report and collected in the CRF. The local reactions collected on the Participant Reported Reactogenicity CRF page will be combined with the 7-day e-diary data and included for the below analysis (presence, maximum severity, onset day, and duration). The main reason for missing e-diary entries (missing when all reactogenicity entries are considered, including any recalled e-diary entries and data entered on the Participant Reported Reactogenicity CRF page) will be collected by the investigator on the Summary of Reactogenicity CRF page.

This section describes derivations with details for the assessment of local reactions: any presence, maximum severity, duration, and onset day of local reactions, in addition to any presence of severe local reactions.

Presence or Absence

For the data summary of the presence (yes or no) of a local reaction during the interval from Day 1 through Day 7 after vaccination, where Day 1 is the day of vaccination, the following variables are required in order to compute the proportions:

- Presence (yes or no) of each severe/Grade 4 local reaction on each day and any day (Day 1 through Day 7).
- Presence (yes or no) of each local reaction by maximum severity on any day (Day 1 through Day 7).

For each local reaction and any local reaction on any day, [Table 3](#) and [Table 4](#) details the algorithm to derive the presence of a reaction (yes or no) during the interval from Day 1 through Day 7, where Day 1 is the day of vaccination.

Table 3. Derived Variables for Presence of Each Local Reaction Within 7 Days After Vaccination

Variable ^a	Yes (1)	No (0)	Missing (.) ^b

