Presence of each local reaction.	Participant reports the reaction as “yes” on any day (Day 1 through Day 7)	Participant reports the reaction as “no” or “I don’t recall” on all 7 days (Day 1 through Day 7) or as a combination of “no,” “I don’t recall,” and missing on all 7 days (Day 1 through Day 7).	Participant does not report any data on all 7 days (Day 1 through Day 7) for the reaction.

- a. The variables will be derived for each of the local reactions (redness, swelling, and pain at the injection site) and for each of the severe local reactions within the interval from Day 1 through Day 7 after vaccination.
- b. "Missing" means missing from both the e-diary and the Participant Reported Reactogenicity CRF page.

Table 4. Derived Variables for Presence of Any Local Reaction Within 7 Days After Vaccination

Variable ^a	Yes (1)	No (0)	Missing (.) ^b
Presence of any local reaction.	Participant reports any local reaction as “yes” on any day (Day 1 through Day 7).	For all 3 local reactions, participant reports “no” or “I don’t recall” on all 7 days (Day 1 through Day 7) or as a combination of “no,” “I don’t recall,” and missing on all 7 days (Day 1 through Day 7).	Participant does not report any data for all 3 local reactions on all 7 days (Day 1 through Day 7).

- a. The variables will be derived for any of the local reactions (redness, swelling, and pain at the injection site) and for any of the severe local reactions within the interval from Day 1 through Day 7 after vaccination.
- b. "Missing" means missing from both the e-diary and the Participant Reported Reactogenicity CRF page.

Severity and Maximum Severity

Redness and swelling will be measured and recorded in measuring device units (range: 1 to 21) and then categorized during analysis as absent, mild, moderate, or severe based on the grading scale in [Table 5](#). Measuring device units can be converted to centimeters according to the following formula: 1 measuring device unit = 0.5 cm. Pain at the injection site will be assessed by the participant as absent, mild, moderate, or severe according to the grading scale in [Table 5](#).

Table 5. Local Reaction Grading Scale

	Mild (Grade 1)	Moderate (Grade 2)	Severe (Grade 3)	Potentially Life-Threatening (Grade 4^a)
Pain at the injection site	Does not interfere with activity	Interferes with activity	Prevents daily activity	Emergency room visit or hospitalization for severe pain

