3.1.2. Systemic Events

The systemic events assessed and recorded in the e-diary are fever, fatigue, headache, chills, vomiting, diarrhea, new or worsened muscle pain, and new or worsened joint pain from Day 1 through Day 7, where Day 1 is the day of vaccination.

If a systemic event persists beyond the end of the 7-day e-diary collection period following vaccination, the participant will be requested to report that information and the corresponding resolution date. The investigator will enter this resolution date on the Summary of Reactogenicity CRF page.

The systemic events collected on the Participant Reported Reactogenicity CRF page will be combined with the 7-day e-diary data and included for the below analysis (presence, maximum severity, onset day, and duration).

The derivations for systemic events will be handled similarly to the way local reactions are handled for presence of the event, severity level, duration, and onset day.

The variables associated with the systemic events will be computed similarly to the way local reactions are computed (see [Section 3.1.1](#)).

1. Presence (yes or no) of each systemic event on each day (Day 1 through Day 7) after vaccination.

2. Presence (yes or no) of each systemic event on any day (Day 1 through Day 7) after vaccination.
3. Presence or absence of each severe/Grade 4 systemic event on each day and any day (Day 1 through Day 7) after vaccination.
4. Maximum severity of each systemic event on any day (Day 1 through Day 7) after vaccination.
5. Presence or absence of any systemic event on any day (Day 1 through Day 7) after vaccination.
6. Duration of each systemic event after vaccination.
7. Onset day of each systemic event after vaccination.
8. Onset day of any systemic event after vaccination.

The symptoms will be assessed by the participant as absent, mild, moderate, or severe according to the grading scale in Table 6.

Table 6. Systemic Event Grading Scale

	Mild (Grade 1)	Moderate (Grade 2)	Severe (Grade 3)	Potentially Life-Threatening (Grade 4^a)
Vomiting	1-2 times in 24 hours	>2 times in 24 hours	Requires IV hydration	Emergency room visit or hospitalization for hypotensive shock
Diarrhea	2 to 3 loose stools in 24 hours	4 to 5 loose stools in 24 hours	6 or more loose stools in 24 hours	Emergency room visit or hospitalization for severe diarrhea

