5.3.1.1. Reactogenicity Data

Completely missing reactogenicity e-diary data (no data from both the 7-day e-diary and the Participant Reported Reactogenicity CRF page) will not be imputed. For derived variables based on reactogenicity data, if any day of the 7-day e-diary data are available, the “any day (Day 1 through Day 7)” data will be considered nonmissing.

The reactogenicity data are collected through the e-diary, which does not allow participants to skip the question. Therefore, for a specific day, as long as the e-diary data are transferred for that day, all of the reactogenicity data for the participant on that day are nonmissing.

For the “I do not recall” data in the e-diary, it will be imputed as “no” as described in [Table 3](#) and [Table 4 in Section 3.1.1](#). No missing reactogenicity data will be imputed other than what is described in [Section 3.1.1](#) and [Section 3.1.2](#).

In summary, for any participant with all 7 days of the e-diary missing (no data from both the 7-day e-diary collection period and the Participant Reported Reactogenicity CRF page), this will not be included in the analysis (ie, assuming MCAR). If only 1 to 6 days of reactogenicity data are available, the reactogenicity data for the missing day(s) are considered as answering “no” for all reactions. This is based on the common assumption that no reports mean no events. See [Table 3](#) and [Table 4](#) for the derivation algorithms.

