6.1.1.2. Sensitivity/Supplementary Analyses

A sensitivity analysis will be conducted for the above summary of reactogenicity events by maximum severity. A variable to indicate the time period from the planned e-diary day (11:59 PM on that calendar day) to the actual time of e-diary reporting will be derived based on FARFTDTC (reference time point, ie, the time of vaccination), FADTC (data collection time), and FATPT (time point of intended solicitation day) in the dataset. The period will be categorized in relation to the planned e-diary day, ie, within the planned day, 1 day out (1-24 hours), 2 days out (>24-48 hours), or 3 days out (>48-72 hours) from the planned e-diary day. The sensitivity analysis will exclude the participants with e-diary reports collected outside the intended solicitation (calendar) day or with data collected from the Participant Reported Reactogenicity CRF page.

To support the assessment of reactogenicity, the endpoints below, as specified in [Section 3.1.1](#) and [Section 3.1.2](#), will be summarized with the same analysis time point and analysis population:

- Duration (days) of each local reaction and each systemic event after vaccination.
- Onset day of each local reaction and each systemic event after vaccination.
- Presence of each and any severe local reaction and each and any severe systemic event on each of the 7 days and for “any day (Day 1 through Day 7).”

The presentation of the results will include a basic descriptive summary without 95% CIs ([Section 5.2](#)).

These continuous endpoints will be summarized by displaying the n, mean, median, standard deviation, minimum, and maximum for each study intervention group.

In addition, the proportions of participants reporting prompted local reactions, by maximum severity level, with any e-diary errors will be included as a supplemental summary.

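### Diary values confirmed as errors are dropped with no stated replacement, so a real but mis-keyed reaction can be scored absent, and the planned with-errors summary leaves out systemic events

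*SAP*

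**What the plan says.** **Errors.** Section 6.1.1.1 of the Substudy A SAP, which covers local reactions and systemic events, says "e-diary data that are confirmed as errors will not be used for analysis". SAPs B and C have the same words. None mentions substituting the right value.

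**Missing days.** Under section 5.3.1.1, when one to six days have data, "the reactogenicity data for the missing day(s) are considered as answering" *no*. Table 3 in section 3.1.1 scores a reaction present if "Participant reports the reaction as “yes” on any day (Day 1 through Day 7"), and absent for any mixture of *no*, not recalled and missing. Section 6.1.1.1 adds "The denominator will be the number of participants reporting at least 1" *yes* or *no* response, so a participant with other diary days stays in N.

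**Retrieval.** For missing local-reaction records, section 3.1.1 says "the data may be retrieved by the investigator via participant report and collected in the CRF". Section 3.1.2 says "The systemic events collected on the Participant Reported Reactogenicity CRF page will be combined with the 7-day e-diary data".

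**What an error is.** Protocol section 10.11.8.10.4 (likewise 10.12.8.10.4 and 10.13.8.10.6) lists the situations in which a site visit is not required after a severe entry. One is "The participant recorded an incorrect value in the reactogenicity e-diary (confirmation of a reactogenicity e-diary data entry error"). The telephone contact is recorded in source and in the CRF.

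**The check.** Section 6.1.1.2 says that "the proportions of participants reporting prompted local reactions, by maximum severity level, with any e-diary errors will be included as a supplemental summary". The other sensitivity analysis in that section removes participants with late or CRF-page reports. It does not address errors.

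**The concern.** The protocol describes the error as a wrong value, and a wrong value is not an absent event. The SAP justifies scoring missing days as *no* by treating silence as absence. Here the participant did report something, and what was wrong may have been only its size.

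Two examples fit the trial's own scales:

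- A participant keys 102.6°F for 100.6°F on the only febrile day. The true reading is still a fever.
- Redness of 11 measuring-device units is keyed as 21. The true grade is moderate.

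If such an entry is removed and nothing replaces it, the derivation can return *no*.

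Presence and maximum severity of these reactions are primary results. For systemic events, no planned output would let a reader see what was removed.

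**Working it through.** **1. The plan's own figures.** The point rests on no figure in the documents. The only calculated figures behind the safety sample size are the chances of seeing at least one event, 1 − (1 − p)^n, in protocol Tables 6 and 8 (n=90) and Table 11 (n=30). At p = 2%: 1 − 0.98^90 = 0.8377 (stated 83.8%) and 1 − 0.98^30 = 0.4545 (stated 45.5%). All ten distinct values reproduce.

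**2. The examples.** (102.6 − 32) × 5/9 = 39.2°C, at or above the 39.0°C that prompts a call (protocol 8.3.4.4). (100.6 − 32) × 5/9 = 38.1°C, above the 38.0°C fever definition. In Table 2 of the protocol, 21 units is severe and 11 units is moderate.

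**3. Table 3 applied to four diaries.**

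| Diary | Result |
|---|---|
| One-day event, entry removed, six other days *no*, nothing retrieved | *no*, stays in N |
| Two-day event, one day removed | *yes* |
| Entry removed, value re-entered on the CRF page | *yes* |
| Only one day transmitted, that entry removed | missing, leaves N |

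Only the first pattern turns a real event into a non-event.

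**4. Multi-day events.** Suppose redness is truly 11 units on Day 2 (keyed as 21) and 6 units on Day 3. With Day 2 removed, maximum severity falls from moderate to mild and onset moves from Day 2 to Day 3. Duration (resolution − start + 1) falls from 3 − 2 + 1 = 2 days to 3 − 3 + 1 = 1 day.

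**5. Does the SAP settle whether a removed entry can be retrieved?** No.

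- Retrieval is optional and written for missing records.
- Section 5.3.1.1 treats every item as nonmissing once that day's diary has been transferred, so a transmitted and later rejected value is not clearly a missing record.
- Section 6.1.1.1 says that intermediate gaps are not imputed, and then that partial gaps become *no*.

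Two programmers could score the same participant differently.

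**6. Size per participant.** 1/90 = 1.1 points (A and B); 1/30 = 3.3 points (C). With Clopper-Pearson 95% intervals:

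- n=90: 2/90 = 2.2% (0.3 to 7.8) becomes 3/90 = 3.3% (0.7 to 9.4).
- n=30: 0/30 = 0% (0 to 11.6) becomes 1/30 = 3.3% (0.1 to 17.2).

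**7. Assumed losses (illustration only).** If 5%, 10% or 20% of true events at a 2% rate were lost, the chance of seeing at least one, 1 − (1 − 0.02 × (1 − loss))^n, would fall from 83.8% to 82.2%, 80.5% or 76.6% (n=90), and from 45.5% to 43.8%, 42.0% or 38.4% (n=30). No document supports any particular loss fraction.

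**The case against.** **Silence is not prohibition.** The SAPs say that wrong values are not used. They do not bar re-collecting the right ones. The CRF page exists, its data are pooled with the diary, and the call is already recorded in the CRF. This stands: the loss is possible, not automatic. It also shows how small the remedy is.

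**Few items are exposed.** Mis-keyed magnitude mainly concerns temperature, redness and swelling; pain and most systemic symptoms are entered as grades. This also stands.

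**The substudies are descriptive.** There are no tests or decision rules, and one changed participant lies well inside the interval. That limits the consequence, but the rates are still the primary results.

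**The local-only summary may be a drafting slip.** Section 6.1.1.1 also refers only to the local reaction when defining a denominator that serves both kinds of event. If so, correcting it is all the easier.

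A reader might also infer that deletions fall only on high values, can only bias rates downward, and do so more in the more reactogenic groups. The documents do not support this:

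- If the participant had no event, removing a false fever corrects the rate.
- Investigators review all diary data frequently (protocol 8.3.4) and again at the 4-week visit, and the Substudy C stopping-rule text on confirmed errors is not limited to severe entries.
- A call about a true Grade 3 event should confirm it, not delete it, and participants and safety evaluators are blinded.

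**Conclusion.** The concern holds in a conditional form. As written, the SAPs allow a real, mis-keyed reaction to be scored absent when the removed entry was the only *yes*, other days have data, and the true value is not retrieved. They do not make that outcome certain. The gap in the summary is unconditional: nothing planned shows deletions for fever or the other seven systemic events.

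The total effect cannot be estimated, because the documents give no error rate. A reader might be tempted to assume one. For example, suppose 3% of participants have a confirmed error on fever, 70% of these have a real milder fever, and 70% of those have it on that day only. That gives 0.03 × 0.70 × 0.70 = 1.47% of participants, or 29% of a 5% true rate. But it requires 0.03 × 0.70 = 2.1% of participants to be febrile with a mis-keyed value, which is 2.1/5 = 42% of all febrile participants. That is not credible, and no relative undercount should be quoted.

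The change is worth making because it is cheap and removes an ambiguity in a primary endpoint.

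**What to change.** In SAPs A, B and C:

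1. **Section 6.1.1.1.** State that a value confirmed as an error is replaced by the corrected value that the investigator obtains and records on the Participant Reported Reactogenicity CRF page, and that *no* is scored only when the investigator confirms that no event occurred.
2. **Section 6.1.1.2.** Widen the with-errors summary from prompted local reactions to prompted local reactions and systemic events.
3. **Flag corrected entries.** The 6.1.1.2 sensitivity analysis excludes anyone with CRF-page data, so corrected participants would drop out of it. A separate flag lets that analysis be interpreted.

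**Cost.** SAP wording, a CRF completion instruction for a contact that already takes place, and one more table. Corrected values rest on recall, as retrieved missing records already do. The SAPs should also say how an event is tabulated when it is confirmed but its size cannot be recovered. Counting it as present with severity missing would need an extra category in the severity tables and bar charts.

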6.1.1.2. Sensitivity/Supplementary Analyses

A sensitivity analysis will be conducted for the above summary of reactogenicity events by maximum severity. A variable to indicate the time period from the planned e-diary day (11:59 PM on that calendar day) to the actual time of e-diary reporting will be derived based on FARFTDTC (reference time point, ie, the time of vaccination), FADTC (data collection time), and FATPT (time point of intended solicitation day) in the dataset. The period will be categorized in relation to the planned e-diary day, ie, within the planned day, 1 day out (1-24 hours), 2 days out (>24-48 hours), or 3 days out (>48-72 hours) from the planned e-diary day. The sensitivity analysis will exclude the participants with e-diary reports collected outside the intended solicitation (calendar) day or with data collected from the Participant Reported Reactogenicity CRF page.

To support the assessment of reactogenicity, the endpoints below, as specified in [Section 3.1.1](#) and [Section 3.1.2](#), will be summarized with the same analysis time point and analysis population:

- Duration (days) of each local reaction and each systemic event after vaccination.
- Onset day of each local reaction and each systemic event after vaccination.
- Presence of each and any severe local reaction and each and any severe systemic event on each of the 7 days and for “any day (Day 1 through Day 7).”

The presentation of the results will include a basic descriptive summary without 95% CIs ([Section 5.2](#)).

These continuous endpoints will be summarized by displaying the n, mean, median, standard deviation, minimum, and maximum for each study intervention group.

In addition, the proportions of participants reporting prompted local reactions, by maximum severity level, with any e-diary errors will be included as a supplemental summary.

